5.2.4.1 Renal function

The estimated glomerular filtration rate (eGFR) will be derived from serum creatinine values, age sex and race based on the Chronic Kidney Disease Epidemiology creatinine (CKD-EPIcr) equation [[R12-1392](#)].

5.2.4.2 Pregnancy testing

Pregnancy testing (urine) will be performed in female patients of child bearing potential according to the time points indicated in the [Flow Chart](#). Pregnancy kits will be provided by the Central Laboratory. For reporting of pregnancy event refer to [section 5.2.7.2](#).

5.2.4.3 Criteria for hypoglycaemic events

All symptomatic hypoglycaemia events, or severe hypoglycaemias (e.g. if the patient required assistance of another person), or any hypoglycaemia episode with glucose values < 54 mg/dl (< 3.0 mmol/l), or if the investigator considered the event to be an AE should be documented as an AE "hypoglycaemic event". In non-diabetic or pre-diabetic patients, the investigator should consider and rule out other alternative causes for such symptoms and can perform blood glucose levels to confirm the diagnosis of hypoglycaemia.

5.2.4.4 Urinary tract infection and genital infections

Patients having a history of chronic/recurrent UTIs or genital infections, or an acute episode of UTI or genital infection at screening will be identified and this condition has to be documented as medical history or baseline condition in the eCRF, respectively.

For documentation of symptomatic acute UTI during trial conduct, a urine culture sample has to be taken and sent to central lab for confirmation of the diagnosis.

5.2.5 Electrocardiogram

12-lead ECGs will be performed at the screening and EOT Visits as indicated in the [Flow Chart](#). The investigator or a designee will evaluate whether the ECG is normal or abnormal and whether it is clinically relevant, if abnormal. ECGs may be repeated for quality reasons and the repeated recording used for analysis.

In case of any cardiac symptom (indicating rhythm disorders or cardiac ischaemia), or for safety reasons additional 12-lead ECG(s) should be done and any abnormal findings will be reported as AEs. Dated and signed printouts of ECG with findings should be documented in patient's medical record.

Clinically relevant abnormal findings will be reported either as baseline condition (if identified at the screening visit) or otherwise as adverse events and will be followed up and/or treated as medically appropriate.

5.2.6 Other safety parameters

There are no additional safety parameters in the trial.

5.2.7 Assessment of adverse events

5.2.7.1 Definitions of AEs

Adverse event

An adverse event (AE) is defined as any untoward medical occurrence in a patient or clinical investigation subject administered a medicinal product and which does not necessarily have to have a causal relationship with this treatment.

An AE can therefore be any unfavourable and unintended sign (including an abnormal laboratory finding), symptom, or disease temporally associated with the use of a medicinal product, whether or not considered related to the medicinal product.

Serious adverse event

A serious adverse event (SAE) is defined as any AE which fulfils at least one of the following criteria:

- results in death,
 - is life-threatening, which refers to an event in which the patient was at risk of death at the time of the event; it does not refer to an event that hypothetically might have caused death if more severe.
 - requires inpatient hospitalisation or
 - requires prolongation of existing hospitalisation,
 - results in persistent or significant disability or incapacity, or
 - is a congenital anomaly / birth defect,
- or
- is deemed serious for any other reason if it is an important medical event when based on appropriate medical judgement which may jeopardise the patient and may require medical or surgical intervention to prevent one of the other outcomes listed in the above definitions.

Examples of such events are intensive treatment in an emergency room or at home for allergic bronchospasm, blood dyscrasias or convulsions that do not result in hospitalisation or development of dependency or abuse.

AEs considered “Always Serious”

In accordance with the European Medicines Agency initiative on Important Medical Events, Boehringer Ingelheim has set up a list of further AEs, which by their nature, can always be considered to be “serious” even though they may not have met the criteria of an SAE as defined above.

The latest list of “Always Serious AEs” can be found in the eDC system. These events should always be reported as SAEs as described above.

Note: Cancers of new histology and exacerbations of existing cancer must be classified as a serious event regardless of the duration between discontinuation of the drug and must be reported as described in [section 5.2.7.2](#), subsections “AE Collection” and **AE reporting to sponsor and timelines”**

Adverse events of special interest

The term adverse event of special interest (AESI) relates to any specific AE that has been identified at the project level as being of particular concern for prospective safety monitoring and safety assessment within this trial, e.g. the potential for AEs based on knowledge from other compounds in the same class. AESIs need to be reported to the sponsor’s Pharmacovigilance Department within the same timeframe that applies to SAEs, please see below.

The following are considered as AESIs:

Hepatic injury

A hepatic injury is defined by the following alterations of hepatic laboratory parameters:

- an elevation of AST and/or ALT ≥ 3 fold ULN combined with an elevation of total bilirubin ≥ 2 fold ULN measured in the same blood draw sample, and/or
- aminotransferase (ALT, and/or AST) elevations ≥ 5 fold ULN

These lab findings constitute a hepatic injury alert and the patients showing these lab abnormalities need to be followed up according to the “DILI checklist” provided in the ISF. In case of clinical symptoms of hepatic injury (icterus, unexplained encephalopathy, unexplained coagulopathy, right upper quadrant abdominal pain, etc.) without lab results (ALT, AST, total bilirubin) available, the investigator should make sure these parameters are analysed, if necessary in an unscheduled blood test. Should the results meet the criteria of hepatic injury alert, the procedures described in the DILI checklist should be followed.

Decreased renal function

Decreased renal function is defined by a creatinine value showing a ≥ 2 fold increase from baseline and is above the ULN.

For the AESI “decreased renal function” patients need to be followed up appropriately based on local clinical guidance.

Ketoacidosis

If metabolic acidosis, ketoacidosis and DKA is suspected further investigations should be done according to the medical judgment and the clinical course until a diagnosis is made and/or the patient is recovered.

Due to its mechanism of action, empagliflozin may potentially modify the clinical presentation of ketoacidosis which may occur at lower plasma glucose levels in patients with DM and potentially also in non-diabetic patient population. The diagnosis of ketoacidosis in these patients can be based on arterial pH ≤ 7.30 , serum bicarbonate levels $< 15\text{mmol/L}$ and measurement of serum beta-hydroxybutyrate levels. Other diagnostic criteria which can support the diagnosis of ketoacidosis are urine ketones and anion gap $>10\text{mmol/L}$.

Investigators should note that not all criteria mentioned above need to apply for the diagnosis of ketoacidosis, and clinical judgment should also be taken into consideration.

Intensity (severity) of AEs

The intensity (severity) of the AE should be judged based on the following:

Mild:	Awareness of sign(s) or symptom(s) that is/are easily tolerated
Moderate:	Sufficient discomfort to cause interference with usual activity
Severe:	Incapacitating or causing inability to work or to perform usual activities

Causal relationship of AEs

Medical judgement should be used to determine the relationship, considering all relevant factors, including pattern of reaction, temporal relationship, de-challenge or re-challenge, confounding factors such as concomitant medication, concomitant diseases and relevant history.

Arguments that may suggest that there is a reasonable possibility of a causal relationship could be:

- The event is consistent with the known pharmacology of the drug.
- The event is known to be caused by or attributed to the drug class.
- A plausible time to onset of the event relative to the time of drug exposure.
- Evidence that the event is reproducible when the drug is re-introduced
- No medically sound alternative aetiologies that could explain the event (e.g. pre-existing or concomitant diseases, or co-medications).
- The event is typically drug-related and infrequent in the general population not exposed to drugs (e.g. Stevens-Johnson syndrome).
- An indication of dose-response (i.e. greater effect size if the dose is increased, smaller effect size if dose is diminished).

Arguments that may suggest that there is no reasonable possibility of a causal relationship could be:

- No plausible time to onset of the event relative to the time of drug exposure is evident (e.g. pre-treatment cases, diagnosis of cancer or chronic disease within days / weeks of drug administration; an allergic reaction weeks after discontinuation of the drug concerned)
- Continuation of the event despite the withdrawal of the medication, taking into account the pharmacological properties of the compound (e.g. after 5 half-lives).
- Of note, this criterion may not be applicable to events whose time course is prolonged despite removing the original trigger.
- Additional arguments amongst those stated before, like alternative explanation (e.g. situations where other drugs or underlying diseases appear to provide a more likely explanation for the observed event than the drug concerned).
- Disappearance of the event even though the trial drug treatment continues or remains unchanged.

5.2.7.2 Adverse event collection and reporting

AE Collection

The investigator shall maintain and keep detailed records of all AEs in the patient files. The following must be collected and documented on the appropriate CRF(s) by the investigator:

- From signing the informed consent onwards until the individual patient's end of trial:
All AEs (serious and non-serious) and all AESIs.
- After the individual patient's end of trial:
The investigator does not need to actively monitor the patient for AEs but should only report related SAEs and related AESIs of which the investigator may become aware of by any means of communication, e.g. phone call. Those AEs should however, not be reported in the CRF.

[figure not shown]

Figure 5.2.7.2: 1 Adverse Event Collection Periods

AE reporting to sponsor and timelines

The investigator must report SAEs, AESIs, and non-serious AEs which are relevant for the reported SAE or AESI, on the BI SAE form via fax immediately (within 24 hours) to the sponsor's unique entry point (country specific contact details will be provided in the ISF). The same timeline applies if follow-up information becomes available. In specific occasions the investigator could inform the sponsor upfront via telephone. This does not replace the requirement to complete and fax the BI SAE form.

With receipt of any further information to these events, a follow-up SAE form has to be provided. For follow-up information the same rules and timeline apply as for initial information.

Information required

For each AE, the investigator should provide the information requested on the appropriate eCRF pages and the BI SAE form, if applicable. The investigator should determine the causal relationship to the trial medication. .

The following should also be recorded as an (S)AE in the CRF and BI SAE form (if applicable):

- Worsening of the underlying disease or of other pre-existing conditions
- Changes in vital signs, ECG, physical examination and laboratory test results, if they are judged clinically relevant by the investigator.

If such abnormalities already pre-exist prior to trial inclusion they will be considered as baseline conditions and should be collected in the eCRF only. All (S)AEs, including those persisting after individual patient's end of trial must be followed up until they have resolved, have been assessed as "chronic" or "stable", or no further information can be obtained.

For some types of AEs additional information will be collected in the eCRF due to the nature of the event and mechanisms of action of the trial medication. These listed AEs are distinct from AESI. The list of types of AEs for which additional information will be collected may change during the trial based on potential new knowledge about the safety profile of empagliflozin:

- Hypoglycaemic event
- Genital infection
- Acute pyelonephritis
- Sepsis
- Urinary tract infection
- Bone fracture
- Hypotension

Pregnancy

In rare cases, pregnancy might occur in a clinical trial. Once a patient has been enrolled in the clinical trial and has taken trial medication, the investigator must report any drug exposure during pregnancy in a trial participant immediately (within 24 hours) by means of Part A of the Pregnancy Monitoring Form to the sponsor's unique entry point.

The outcome of the pregnancy associated with the drug exposure during pregnancy must be followed up and reported to the sponsor's unique entry point on the Pregnancy Monitoring Form for Clinical Trials (Part B).

The ISF will contain the Pregnancy Monitoring Form for Clinical Trials (Part A and B).

As pregnancy itself is not to be reported as an AE, in the absence of an accompanying SAE and/or AESI, only the Pregnancy Monitoring Form for Clinical Trials and not the SAE form is to be completed. If there is an SAE and/or AESI associated with the pregnancy an SAE form must be completed in addition.

5.3 DRUG CONCENTRATION MEASUREMENTS AND PHARMACOKINETICS

5.3.1 Assessment of pharmacokinetics

This study will not analyse pharmacokinetic or pharmacodynamics parameters.

5.4 ASSESSMENT OF BIOMARKER(S)

This study will not analyse exploratory biomarkers. Please refer to [section 5.1.4](#) for details on NT-proBNP.

5.5 OTHER ASSESSMENTS

5.5.1 Echocardiogram

An echocardiogram will be performed on all patients as part of the screening procedures. The standard methodology of the institution will be used and the following clinical information will be recorded:

- Left Ventricular Ejection Fraction
- Left ventricular end-diastolic and end-systolic diameters
- Left ventricular end-diastolic and end-systolic volumes
- Wall motion abnormalities (if any)
- Septal and posterior wall thickness
- Left Atrium (LA) diameter
- Heart valve status
- Any other abnormal findings (according to investigator judgement)

Optional measurements:

- LV mass index (LVMI)
- E/e'
- LA volume
- LA area

For details on echocardiographic parameters please refer to [appendix 10.7](#).

5.5.2 Health Care Resource Utilisation (HCRU)

HCRU will be captured via interview with the patient and verified against medical records where available and entered in the eCRF at the visits specified in the [Flow Chart](#). Information on utilization of following resources will be collected:

- All-cause hospital admissions (first and recurrent)
- Hospital admission due to worsening of chronic heart failure (first and recurrent)
- All-cause emergency room visits (first and recurrent)
- Emergency room visits due to worsening of chronic heart failure (requiring i.v. diuretic therapy) (first and recurrent)
- Any unscheduled outpatient visits (first and recurrent)
- Unscheduled outpatient visits related to heart failure (first and recurrent)

5.6 APPROPRIATENESS OF MEASUREMENTS

The primary endpoint measurement will be consistent with the recognized standard for conducting the 6MWT to assess treatment changes in heart failure patients ([R03-0725](#)).

All secondary and further endpoint measurements performed during this trial are standard measurements and will be performed in order to determine empagliflozin efficacy in an appropriate way. The scheduled measurements are appropriate to see drug induced changes in vital signs, standard laboratory values and biomarkers specific to efficacy of treatment of HF. The endpoints are widely used and accepted for evaluation of efficacy on an oral HF drug.

Patient Reported Outcome measures are an essential part for this phase III trial.

Therefore, the appropriateness of all measurements applied in this trial is given.

6. INVESTIGATIONAL PLAN

6.1 VISIT SCHEDULE

All patients are to adhere to the visit schedule as specified in the [Flow Chart](#). If any visit has to be rescheduled, subsequent visits should follow the original visit date schedule. The trial medication packs contain sufficient medication to allow for these time windows.

All trial visits should take place at approximately the same time of day and preferably before noon.

6.2 DETAILS OF TRIAL PROCEDURES AT SELECTED VISITS

Please refer to the [Flow Chart](#) and [section 5](#) for details of the procedures performed at each visit.

6.2.1 Screening and run-in period(s)

Screening Period

Following informed consent, the patient will undergo visit 1/screening assessments as indicated in the [Flow Chart](#). The assessments must all fall within the acceptable screening visit window but do not need to be performed on the same day. The patient should be registered in IRT as a screened patient.

For patients with no BNP or NT-proBNP measurement available from clinical routine in the past 6 months indicative of the likelihood of eligibility for this study, it is recommended to split the screening visit into two steps and start with the measurement of NT-proBNP and safety lab measures (via central laboratory), wait for the results, and do the remaining screening assessments on a separate day (within the allowed visit window)

One 6MWT will be performed at the screening visit (visit 1) to assess patient eligibility and if the distance walked during the 6MWT is > 350m, the patient will be considered a screen failure. If the distance walked during the 6MWT is < 100m at screening, the patient is allowed to return to the baseline assessment to account for a learning effect that may result in some improvement of the walking distance.

If the patient meets the entry criteria, Visit 2 should occur as soon as possible once it has been confirmed that the patient is eligible to continue. If the patient does not meet the entry criteria, (i.e. fail to meet one or more of the inclusion criteria, and/or meet one or more of the exclusion criteria) following Visit 1 procedures, they should be registered as a screen failure in IRT.

Re-testing for certain eligibility criteria can be performed once for abnormal laboratory, blood pressure and / or ECG results as outlined in [section 3.3](#). Rescreening will be considered on a case-by-case basis as described in [section 3.3](#).

6.2.2 Treatment period(s)

Randomisation will occur at Visit 2 using IRT. The patients will return to the clinic for regularly scheduled visits 6 and 12 weeks after randomisation as specified in the [Flow Chart](#). These on-site visits will assess the occurrence of safety and efficacy endpoints, trial medication compliance, concomitant therapy or intervention.

All Visit 2 assessments must be performed before the first dose is taken at the site. The assessments at Visits 3 and 4 must be performed post-dose. Patients should be instructed to take their medication on the morning of trial Visits 3 and 4. Visits should be routinely scheduled at approximately the same time of day for each visit.

At all treatment visits (Visits 2, 3 and 4/EOT) and the early discontinuation visit, patient reported outcome measures should be completed first.

Patient reported outcome measures should be completed in the following order:

- KCCQ
- PGI – Severity – Heart Failure Symptoms
- PGI – Change – Heart Failure Symptoms
- PGI - Severity - Dyspnea
- PGI - Change – Dyspnea
- CHQ-SAS

The order of the remaining assessments should be preferably completed as follows and according to the visits specified in the [Flow Chart](#):

- Physical examination, body weight, height and vital signs
- Completion of clinician impression scales and clinical congestion score by Investigator
- ECG
- 6MWT conducted in duplicate (at visits 2 and 4 only) at least 1 hour apart. At visits 1, 3 and the early discontinuation visit, only one 6MWT will be conducted.
- Laboratory sample, urine pregnancy

Testing of the 6MWT at each clinic visit should be performed about the same time of day to minimize intraday variability. Prior to performing the 6MWT the relative contraindications to exercise should be assessed as per [appendix 10.1.3](#).

All other medications the patient is receiving should be taken as instructed by the physician.

At any time during the treatment period the HF background therapy is allowed to be

adjusted and optimised according to local and international guidelines.

If any additional therapy is considered necessary for the patient's welfare during the treatment period it may be given at the discretion of the Investigator (see also restrictions in [section 4.2.2](#)).

Patients will be dispensed medication at visits 2 and 3 and allocation of new kit number(s) will be managed through the IRT. Visit 4 is the last day of treatment and the patient should return all remaining medication during this visit.

Permanent trial medication discontinuation is only justified when clear persistent contraindications arise, or when the patient requests to stop trial medication. See [section 3.3.4.1](#) for details on how to handle trial medication discontinuations.

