5.2.3 Body weight and height

Measurements of body weight and height will be performed at the time points specified in the [Flow Chart](#).

Body Mass Index (BMI) (kg/m²) will be calculated for determination of eligibility at Visit 1.

Body weight should be measured as follows:

- after the urine sampling (weight after bladder voiding),
- shoes and coat/jackets should be taken off, and
- pockets should be emptied of heavy objects (i.e. keys, coins etc.).

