5.2.4 Safety laboratory parameters

Safety laboratory parameters to be assessed are listed in [table 5.2.4.1](#). For the sampling time points please see the [Flow Chart](#).

All analyses will be performed by a central laboratory, the respective reference ranges will be provided in the ISF.

Patients do not have to be fasted for the blood sampling for the safety laboratory. Instructions regarding sample collection, sample handling/ processing and sample shipping are provided in the Laboratory Manual in the ISF.

The central laboratory will send reports to the investigator. It is the responsibility of the investigator to evaluate the laboratory reports. Clinically relevant abnormal findings as judged by the investigator will be reported as adverse events (please refer to [section 5.2.7.1](#)).

In case the criteria for hepatic injury are fulfilled, a number of additional measures will be performed (please see [section 5.2.7.1](#) and the DILI Checklist provided in the ISF and electronic data capture (eDC) system. The amount of blood taken from the patient concerned will be increased due to this additional sampling.

The central laboratory will transfer the results of the analysis to the sponsor.

Table 5.2.4:1 Safety laboratory tests

Haematology

• Hematocrit• Haemoglobin
- Reticulocyte Count (reflex test if Hb outside normal range)• Red Blood Cells (RBC) / Erythrocytes• WBC / Leukocytes• Platelet Count / Thrombocytes• Differential Automatic (relative and absolute count): Neutrophils, Eosinophils, Basophils, Monocytes, Lymphocytes
Clinical chemistry

• Albumin• Alkaline phosphatase
- γ-GT (gamma-glutamyl transferase) reflex test triggered by elevated alkaline phosphatase on two sequential measures• ALT (alanine transaminase, SGPT)• AST (aspartate transaminase, SGOT)• Bicarbonate• Bilirubin total, fractionated if increased• Chloride• Creatinine• Creatine kinase (CK)• Hs Troponin I (reflex tests if CK is elevated)• Glucose• Potassium• Protein total

• Sodium• Urea (BUN)• Uric acid
Urine

• Urinalysis: standard dipstick test including ketones semi-quantitative measurement

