7.6.3 Continuous endpoints

Further continuous endpoints are generally analysed in a mixed model with repeated measures (MMRM), including visit-by-treatment interaction and baseline-by-visit interaction. An unstructured covariance structure will be used to model the within-patient errors. The MMRM analyses will also be shown graphically.

Descriptive statistics will be calculated for the value at visit and change from baseline.

- Change from baseline in KCCQ overall summary score, CSS, and individual domains at Week 6 and week 12
- Change from baseline in CHQ individual domains at week 6 and week 12
- Change from baseline in SBP at Week 6 and week 12
- Change from baseline in DBP at Week 6 and week 12

The following endpoint is assessed as part of the main analysis or sensitivity analysis of the corresponding secondary endpoint:

- Change from baseline in KCCQ TSS at Week 6
- Change from baseline in CHQ-SAS dyspnea at Week 6
- Change from baseline in Clinical Congestion Score at week 6.
- Change from baseline in NT-proBNP at week 6.

Since bodyweight is only measured at baseline and week 12, an ANCOVA model will be presented including baseline weight as a covariate.

Descriptive statistics are planned for:

- Change from baseline to week 6 and week 12 in patient-rated assessment of dyspnea and fatigue by the Borg scale as part of the 6MWT

For the following parameters measured at the follow-up visit, additionally descriptive statistics at baseline, last value on treatment and follow-up will be presented for patients with valid measurements at all three timepoints. .

- SBP
- DBP

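### Protocol 5.2.3 asks for body weight after urine sampling, but the preferred visit order in 6.2.2 puts weight near the start and the laboratory and urine samples last

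*Protocol*

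**What the plan says.** Protocol 5.2.3 sets the method for weighing. It opens with "Body weight should be measured as follows", and its first condition is that weight is taken "after the urine sampling (weight after bladder voiding").

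Protocol 6.2.2 sets the sequence at the treatment visits. Questionnaires come first. For everything else the text is "The order of the remaining assessments should be preferably completed as follows", followed by five steps. The first is "Physical examination, body weight, height and vital signs". Clinician scales, ECG and walk test come next; the walk test line reads "6MWT conducted in duplicate (at visits 2 and 4 only) at least 1 hour apart". The fifth and last step is "Laboratory sample, urine pregnancy".

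The safety laboratory table in Protocol 5.2.4 includes a urine entry: "Urinalysis: standard dipstick test including ketones semi-quantitative measurement".

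SAP 4.1 adds body weight to the analysed endpoints. Because it is measured only at baseline and Week 12, SAP 7.6.3 states that "an ANCOVA model will be presented including baseline weight as a covariate".

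**The concern.** Read literally, the two protocol sections cannot both be followed at a visit where weight and urinalysis are both due. One puts the urine sample before the scales; the other puts it after everything else. Some sites may work from the visit sequence and some from the method section, and one site may do different things at a patient's two visits. Urine still in the bladder then enters the recorded weight at some weighings and not at others.

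At stake is the precision of one added endpoint. There is no scheduled weighing between baseline and Week 12 to average out error. The conflict would also be hard to see afterwards: the SAP's list of important protocol deviations has an assessment-order item for the questionnaires (G3.50) but none for weight.

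**Working it through.** No figure in the plan is in dispute, so the check compares the passages.

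1. **Position in the order.** In Protocol 6.2.2, weight is in step 1 of 5 after the questionnaires, and the laboratory and urine samples are step 5 of 5. Protocol 5.2.3 needs the reverse.

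2. **Does step 5 cover urinalysis?** Its wording names urine only for the pregnancy test, which applies to women of childbearing potential. However, the dipstick is part of the safety laboratory (Protocol 5.2.4), and no other step provides for it. The natural reading is that step 5 includes urine collection for all patients.

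3. **Do the two meet at the same visit?** In the Flow Chart, weight is due at Visits 1, 2, 4 and early discontinuation. Urinalysis is due at Visits 1, 2, 3, 4, early discontinuation and follow-up. Both therefore fall at Visit 2 (baseline) and Visit 4 (Week 12). They also coincide at the early discontinuation visit, whose weight can fall in the Week 12 window in SAP Tables 6.7: 2 and 6.7: 3.

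4. **Is there reconciling text?** None was found: no earlier urine sample and no separate void before weighing. Protocol 6.2 does refer sites to the Flow Chart and section 5 for procedure details.

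5. **What it does to the analysis.** Let u2 and u4 be the weight of retained urine at Visits 2 and 4. Then

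   measured change = true change + (u4 − u2).

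   The added variance is Var(u4) + Var(u2) − 2·Cov(u2, u4). It is zero if every patient voids first and positive when retained urine varies between a patient's visits. By randomisation, u2 has the same expected value in both arms, so a between-arm bias would require the mean of u4 to differ by arm. The documents give no retained volume, time since last void or arm difference for u2 or u4. Neither the variance nor a bias can be given a number.

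**The case against.** The strongest reply is that nothing mandatory is broken. The 6.2.2 sequence is only a preference, 5.2.3 is the specific rule for weighing, and 6.2 points sites to section 5 for detail. A site that collects urine first departs from a preference and meets the measurement rule. This stands, and it limits the point to sites that follow the listed order. It does not remove the point: a recommended order should not lead sites away from the protocol's own method.

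Two stronger readings are tempting.

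- **That patients are weighed before voiding.** The order implies weighing before the urine sample. A patient may void beforehand without a sample being kept, and 6.2.2 does not fix when voiding occurs. Section 5.2.3 links sampling and voiding, so weighing with an unemptied bladder is possible, but it is not established.

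- **That weight loss on empagliflozin is masked.** The protocol describes an osmotic diuresis, and Visit 4 assessments are post-dose, so a fuller bladder on active drug might be inferred. But greater urine production may simply mean more frequent voiding. Bladder content at the scales depends on when the patient last voided, which is not recorded in either document. Both arms follow the same order under blinding, at about the same time of day. The documents do not support a direction, still less a size in kilograms.

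**Conclusion.** The inconsistency is real and minor. A site that follows the preferred order at Visits 2 and 4 takes weight before the urine sample, contrary to 5.2.3, and possibly before voiding. This rests on reading the last step of the order as including urinalysis, which the safety laboratory table supports.

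The likely effect is additional noise in body weight change from uneven practice across sites or visits, of a size the documents do not allow to be estimated. No directional between-arm bias is shown. Weight is an added further endpoint with no place in the testing hierarchy, so no confirmatory conclusion depends on it.

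**What to change.** In Protocol 6.2.2, insert urine collection (urinalysis and, where applicable, the pregnancy test) ahead of body weight. Keep the questionnaires first and leave blood sampling where it is. The questionnaires-first rule and deviation G3.50 are then unaffected, and the sequence agrees with 5.2.3.

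The cost is one line in the visit order and a note to sites, with no added procedure. If weights have already been collected, no re-analysis is needed; the report should state beside the weight results that voiding status at weighing was not standardised.
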